#### **3.4** Calculation or derivation of safety variable(s)

The following safety data will be collected: vital signs, physical examination, 12-lead ECG, haematology, clinical chemistry, urinalysis, and reported AEs.

Change from baseline to each post-baseline time point where scheduled assessments were made will be calculated for relevant measurements.

#### **3.4.1** Adverse events

Adverse events experienced by the subjects will be collected throughout the entire study and will be coded by the AstraZeneca designee using the latest version of the Medical Dictionary for Regulatory Activities (MedDRA).

Adverse event data will be categorized according to their onset date into the following study periods:

- AEs occurring during run-in (onset date  $\geq$  Visit 1 and before the first dose of IP)
- AEs occurring during treatment (onset date  $\geq$  the first day of IP and  $\leq$  the last day of IP + 2 weeks)
- AEs occurring post-treatment (onset date > the last day of IP + 2 weeks and  $\leq$  Visit 11 (Week 26))

The timing of AEs will be assigned to the period in which they first occurred. If an AE has a missing onset date, then unless the stop date of the AE indicates otherwise, this will be considered an on treatment event. Similarly, if an AE has a partial onset date, then unless the partial onset date or the stop date indicates otherwise, this will be considered an on treatment AE. The same 'during treatment' definition will be used for laboratory and physical examination data, where applicable.

#### **3.4.2** Safety topics of special attention

Although the CSP did not describe AEs of special interest, AstraZeneca Patient Safety and study physicians will review all AEs and identify those that merit special attention. These AEs fall into three categories, AEs possibly related to administration of biologics (e.g., anaphylaxis/hypersensitivity reactions and injection site reactions), AEs possibly related to the mechanism of action of tralokinumab as an IL-13 blocking agent (e.g., infections such as

severe, viral, invasive fungal, and parasitic, malignancy, cardiovascular/cerebrovascular events, pregnancy/spontaneous abortion and increased eosinophils) and AEs reported for other biologics in this class (e.g., musculoskeletal). AEs falling into the category of safety topics of special attention will be tabulated.

#### 3.4.3 Laboratory variables

Blood and urine samples for determination of clinical chemistry, haematology and urinalysis parameters will be taken at the times detailed in the CSP. Blood samples for determination of haematology/haemostasis and clinical chemistry will be performed at a central laboratory. Urine samples will be analyzed locally and sent for analysis at the central lab only when a positive dipstick result for any parameter is observed. The parameters outlined in Table 2 in Section 5.2.1 of the CSP, will be collected. Laboratory data will be reported in SI units.

Changes in haematology and clinical chemistry variables between baseline and each subsequent scheduled assessment will be calculated.

Absolute values will be compared to the relevant reference range and classified as low (below range), normal (within range or on limits) or high (above range). The AstraZeneca extended reference ranges will be used for laboratory variables (where they exist). All values (absolute and change) falling outside the reference ranges will be flagged.

Urinalysis data will be categorised as negative (0), trace, or positive (+) at each time-point.

For the purposes of haematology, clinical chemistry and urinalysis shift tables on-treatment will be defined as the latest non-missing assessment whilst the subject is ongoing on treatment, using the 'during treatment' definition as defined in Section 3.4.1.

For the liver function tests: Aspartate Aminotransferase (AST), Alanine Aminotransferase (ALT), Alkaline phosphatase (ALP), S-Gamma-glutamyl transpeptidase (GGT) and total bilirubin (TBL), the multiple of the AstraZeneca upper limit of the normal (ULN) (not extended) range will be calculated for each data point.

i.e., if the ALT value was 72 IU/L (ULN 36) then the multiple would be 2.

Subjects who meet any of the following criteria at any point during the study will be flagged:

- AST  $\ge$  3x ULN
- ALT  $\ge$  3x ULN
- TBL  $\geq 2xULN$

#### 3.4.4 ECGs

Twelve-lead ECG measurements will be recorded in accordance with the protocol.

The outcome of the overall evaluation is to be recorded as normal/abnormal in the electronic case report form (eCRF), with any abnormalities being recorded as not clinically significant or clinically significant.

#### 3.4.5 Physical examination

Complete and brief physical examinations will be performed at time points specified in Table 1 in the CSP. What is included in the assessment will be dependent on whether the examination is complete or brief, as described in Section 5.1.7 of the CSP. For the brief physical examination, only information on whether the assessment was performed or not will be recorded.

Each component of the baseline visit complete physical examination will be recorded as normal or abnormal. Each component of the follow-up complete physical examinations will be recorded as normal, same as baseline, or new/aggravated.

On-treatment will be defined as the latest non-missing assessment whilst the subject is ongoing on treatment, using the 'during treatment' definition as defined in Section 3.4.1.

# **3.4.6** Any new finding(s), or aggravated existing finding(s), judged as clinically significant by the Investigator, will be reported as an AE. Vital signs

Pre-dose vital signs (pulse, systolic blood pressure, diastolic blood pressure, respiration rate and body temperature) will be obtained in accordance with the schedule provided in Table 1 in the CSP.

Changes in vital signs variables between baseline and each subsequent scheduled assessment will be calculated.

Absolute values will be compared to the relevant reference range and classified as low (below range), normal (within range or on limits) or high (above range). All values (absolute and change) falling outside the reference ranges will be flagged.

Body mass index (BMI) will be summarised from the height (in meters) and weight (in kilograms) as follows:

#### $BMI = kg/m^2$

#### 3.4.7 Medical History

The principal for imputing incomplete diagnosis dates when calculating the number of years since diagnosis (earliest possible date) is shown in the table below:

Table 2         Approach to incomplete diagnosis dates for medical history		
Date of Birth	Diagnosis Date	Date for use in calculations
(Year-Month-Day)	(Year-Month-Day)	(Year-Month-Day)
1951-09-16	1951-10-10	1951-10-10
1951-09-16	1951-10-UK	1951-10-01
1951-09-16	1951-UK-UK	1951-10-16
1951-09-16	1952-UK-UK	1952-01-01

## Table 2 Approach to incomplete diagnosis dates for medical history

UK=Unknown

# **3.5** Calculations or derivation of Pharmacokinetic and Immunogenicity variables

Blood samples (processed to serum) for PK and immunogenicity assessments will be collected from all subjects at baseline prior to first IP administration at Week 0 (Visit 3) and at Week 12 (Visit 9) before IP administrations (except for visit 9, where there is no drug administration). ADA assessments will be conducted utilizing a tiered approach (screen, confirm, titer). These validated methods are conducted using a bridging assay format and statistically determined floating screening assay cut point factor and confirmatory assay cut point. The minimal sample dilution is 1:13. Titer values are reported as the reciprocal of the highest dilution that yields a value above the cut point. Samples from pre-defined study time points that confirm positive for ADA will also be tested for neutralizing ADA (nAb) activity. Both ADA and nAb will be summarized using descriptive statistics as described in Section 4.2.9.67.

#### Pharmacokinetics and immunogenicity of tralokinumab:

Tralokinumab serum concentrations will be tabulated by visit along with descriptive statistics. Population PK modelling may also be performed to better characterize the PK of tralokinumab, but will be reported separately from the CSR.

If possible and if relevant, the impact of ADA occurrence on the PK and PD and safety will be summarized in the CSR.

#### 4. ANALYSIS METHODS

#### 4.1 General principles

The analysis of the study endpoints will include all data captured during the 12-week doubleblind treatment period. This includes data regardless of whether IP was prematurely discontinued or delayed, and/or irrespective of protocol adherence, unless the subject withdraws consent to study participation.
Only exacerbations confirmed to meet the protocol definition (CSP Section 5.1.12) will be included in exploratory summaries. This includes only exacerbations that started on or after the date of randomisation, and those that are defined as a worsening of asthma that leads in at least one of the three criteria detailed in protocol Section 5.1.12 being fulfilled. This will include exacerbations where the eCRF exacerbation records a new/worsened symptom, requiring systemic corticosteroid intervention or hospitalization.

A summary table which counts subjects who have been incorrectly randomized and who received incorrect treatment will be presented.

Summary data will be presented in tabular format by treatment. Categorical data will be summarized by the number and percentage of subjects in each category. Continuous variables for parametric data will be summarized by descriptive statistics including N, mean, standard deviation (SD), geometric mean, SD of log values, median, minimum and maximum. All data will be listed. Data listings will be sorted by treatment and subject number.

Measures of location (mean, geometric mean, median, minimum and maximum) will be reported to the same degree of precision as the raw data unless otherwise stated. Measures of spread (SD) will be reported to one further degree of precision.

Continuous descriptive statistics for the percent and absolute change from baseline will summarize N, mean, SD, median, minimum and maximum and will be based on raw data. Continuous descriptive statistics for the ratio will summarize N, geometric mean and SD of log values and will be based on log-transformed data. Primary and secondary efficacy variables will summarise the ratio, absolute and percent change, exploratory efficacy variables will summarise absolute and percent change, and non-efficacy summary statistics on the change from baseline will only present the absolute change.

The primary and secondary variables will be analysed using geometric means. Both the difference in number and the % change or ratio will be reported, but the statistical analysis will only be based on the ratio. All hypothesis testing will be reported using 2-sided tests. P-values will be rounded to 4 decimal places. No adjustment for multiplicity will be performed and nominal p-values will be reported.

For the efficacy analyses except PRO/ SNOT-20 data, if the value of the ratio of Week 12 to baseline is zero and both Week 12 and baseline are not missing, the ratio will be replaced, for the analysis of ratio only (including for descriptive statistics), by half the smallest observed ratio among the randomized subjects with non-zero values (both treatment arms). For the corresponding non descriptive analyses on the ratio, values of baseline equal to zero were replaced by half the smallest observed value among the subjects with non-zero for the calculation of the baseline logtransformed covariate,

For the efficacy analyses except PRO/ SNOT-20 data, if the baseline value is zero, the baseline will be replaced, for the analysis of ratio to baseline or percent change from baseline only (including for descriptive statistics), by half the smallest observed value among the randomized subjects with non-zero values and among all records (baseline and post baseline

for both treatment arms). If both the baseline and post-baseline record are zero, then the percent change is zero.

QQ plots of residuals of the primary and secondary efficacy analysis models (both on absolute change and log-transformed ratio) will be created.

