## 8.2 Sample size estimate

The study is powered to show a reduction in airway submucosal eosinophils, from baseline to week 12 for tralokinumab, versus placebo in the overall study population.

The sample size is based on the primary endpoint; change from baseline to Week 12 in airway submucosal eosinophils. Given the assumed deviation of the log values in the two treatment groups are 1.62 and 1.82, it is estimated that 31 subjects in each treatment arm will be sufficient to achieve at least 80% power to detect a 3.5-fold difference versus placebo using a two-sided test at 5% significance level. With these assumptions the smallest difference that will yield a significant result is a 2.4-fold difference. The assumptions are based on the change in number of eosinophils per mm² subepithelial tissue in bronchial biopsies in studies D5890C00003 (Budesonide/ formoterol) (Pavord ID et al 2009) and MI-CP166 (Laviolette M et al 2013). Though there are some differences between the design of these studies and MESOS, they are considered the most relevant available studies.

It is assumed that a non-neglectable proportion of the subjects will not have an evaluable primary endpoint value due to failed biopsies. To account for this, 40 subjects will be randomized in each treatment arm.

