## 8.5 Methods for statistical analyses

The main focus for the statistical analyses is to compare tralokinumab to placebo with regards to primary key secondary, and safety objectives.

The analysis of the study endpoints will include all data captured during the 12-week doubleblind treatment period. This includes data regardless of whether study treatment was prematurely discontinued or delayed, and/or irrespective of protocol adherence, unless the subject withdraws consent to study participation.

The statistical analyses will compare tralokinumab to placebo. Summary data will be presented in tabular format by treatment. Categorical data will be summarized by the number and percentage of subjects in each category. Continuous variables for parametric data will be summarized by descriptive statistics including N, mean, standard deviation (SD), geometric mean, SD of log values, median, and range. All data will be listed and data listings will be sorted by treatment and subject number.

The primary and secondary variables will be analysed using geometric means. Geometric mean is often used to evaluate data covering several orders of magnitude, and for evaluating ratios, percentages, or other data sets bounded by zero. A geometric mean, unlike an arithmetic mean, tends to dampen the effect of very high or low values, which might bias the mean if an arithmetic mean was calculated. The geometric mean is also a log-transformation of data to enable meaningful statistical evaluations; it accounts for some of the expected skewness in the data, but with the possibility to use a parametric analysis with a p-value directly linked to the confidence interval for the treatment effect. Both the difference in number of cells and the %change or ratio will be reported, but the statistical analysis will only be based on the ratio. Nonparametric analyses will be applied as sensitivity analyses.

All hypothesis testing will be reported using 2-sided tests. Nominal p-values will be reported for primary and secondary variables i.e., no adjustment of multiplicity will be performed. P-values will be rounded to 3 decimal places.

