## **1.3** Number of subjects

The study is powered to show a reduction in airway submucosal eosinophils, from baseline to Week 12 (Visit 9) for tralokinumab, versus placebo in the overall study population.

The sample size is based on the primary endpoint; change from baseline to Week 12 (Visit 9) in airway submucosal eosinophils. Given an assumed deviation of the log values in the 2 treatment groups are 1.62 and 1.82 it is estimated that 31 subjects in each treatment arm will be sufficient to achieve at least 80% power to detect a 3.5-fold difference versus placebo using a two-sided test at 5% significance level. It is assumed that a non-neglectable proportion of the subjects will not have an evaluable primary endpoint value due to failed biopsies. To account for this, 40 subjects will be randomized in each treatment arm.

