## 4.2.4 Analysis of the primary variable

All analyses of the primary endpoint will be based on the FAS.

The primary efficacy variable is the change, expressed as a ratio [Week 12 (Visit 9)/baseline] from baseline to Week 12 (Visit 9) in airway submucosal eosinophils and the primary analysis is to compare this change from baseline to Week 12 (Visit 9) for tralokinumab with placebo.

The primary efficacy variable will be evaluated through the hypothesis test:

H0: ratio (tralokinumab/placebo) equals 1 *vs*. H1: ratio does not equal 1.

The null hypothesis  $(H_0)$  is that the change in airway submucosal eosinophils at Week 12 on tralokinumab is equal to the corresponding change on placebo. The alternative hypothesis  $(H_1)$  is that the change in airway submucosal eosinophils during the 12-week double-blind treatment period is different on tralokinumab compared with the change in airway submucosal eosinophils during the 12-week double-blind treatment period on placebo.

The change in airway submucosal eosinophils in the tralokinumab group will be compared to that seen in the placebo group using an ANCOVA model.

The response variable in the model will be change, on the log-scale (expressed as a ratio) in the number of airway submucosal eosinophils from baseline to Week 12 (Visit 9) [Week 12 (Visit 9)/baseline]. The model will include treatment group as fixed effect and baseline log value as a continuous covariate. No interaction terms will be included in the model. The analysis will be performed using log-transformed data. All group comparisons from ANCOVA model will be based on Type III sums of squares. Estimated geometric means (original scale) will be presented for each treatment group as well the ratio of geometric means for the comparison of tralokinumab versus placebo (tralokinumab/placebo) and corresponding 95% confidence interval (CI).

Available values at both baseline and Week 12 (Visit 9) are required for a subject to be included in the analysis.

Summary statistics for the absolute and percentage change from baseline to Week 12 (Visit 9) will also presented.

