# 6. CHANGES OF ANALYSIS FROM PROTOCOL

A number of clarifications and minor corrections have been made and are listed below:

- Section 3.4.3/4.2.9.2: due to the way the data is collected on the eCRF, the urinalysis categories have been updated to negative, trace or positive.
- The presentation of asthma exacerbations is not detailed in the protocol. This has been added as an exploratory variable (Section 1.1.4) and some text detailing summaries that will be provided have been included In addition, a start and end date definition of an exacerbation has also been added.
- Section 3.3.1.5: Categorisation of Improved/ No Change/ Deterioration has be relabelled as ACQ-6 Response to be distinct from ACQ-6 Responder which is Yes or No.
- Section 1.1.4 p.15: The analysis is now calculate the change from baseline up to Week 12 in fractional exhaled nitric oxide ( $FE_{NO}$ )
- Section 3.1.1: Baseline for Asthma Daily Diary variables will be, for each variable, the average of all the daily records within the 14 days prior to randomization
- Section 3.2.3.1 to Section 3.2.3.3: ratios will also be calculated for sputum, serum, large and small airways remodelling variables
- Section 3.3.1.3: Bi-weekly mean number of nights is expressed as a percentage
- Section 3.4.1 and 4.2.2: increased follow-up period to 20 weeks
- Section 1.1.4 and 3.2.3.2, 3.2.3.3: The three types of change from baseline analyses (absolute, percent, ratio) will be performed for all exploratory endpoints.
- Section 3.2.3.1: Removed analysis of soluble biomarkers, serum biomarker, nasosorption biomarkers, airway epithelial gene expression, airway volume and resistance based on FRI, effect of Tralo on RNA.
- Removed references to sub-sub segmental as team will be combining sub-segmental and sub-sub-segmental analyses together.
- SNOT-20 is coming from RAVE, and not from the e-diary data.
- The change in sputum eosinophils as percentage number of inflammatory cells won't be analysed (this was a supportive secondary outcome measure added in protocol amendment 2).
- MMRM only performed on secondary efficacy; not on efficacy

- Section 2.1.3: The definition of PK analysis set has been updated to include subjects in FAS who received tralokinumab and had blood samples obtained for PK.
- Section 3.4.2: The OAEs have been updated to safety topics of special attention
- Section 4.1: Under general principles, the p-values rounding has been updated from 3 to 4 decimal places (reference CSP section: 8.5).

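### SAP 4.1 prints the arithmetic mean and SD of raw percent change, which is badly skewed at the plan's own log SDs, and its text conflicts with Section 6 on whether exploratory variables also get a ratio summary.

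*SAP*

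**What the plan says.** SAP 3.1.2 defines percent change as the post-randomization value minus baseline, divided by baseline, times 100. That equals 100 × (ratio − 1), so percent change and ratio carry the same information.

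SAP 4.1 summarises the two differently. For percent change: "Continuous descriptive statistics for the percent and absolute change from baseline will summarize N, mean, SD, median, minimum and maximum", calculated on raw data. For the ratio it lists N, geometric mean and SD of the log values. It then allocates them: "Primary and secondary efficacy variables will summarise the ratio, absolute and percent change, exploratory efficacy variables will summarise absolute and percent change". SAP 4.2.4 repeats the percent-change summary for the primary variable: "Summary statistics for the absolute and percentage change from baseline to Week 12 (Visit 9) will also presented".

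Protocol 8.5 explains why geometric means were chosen: "A geometric mean, unlike an arithmetic mean, tends to dampen the effect of very high or low values, which might bias the mean".

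For exploratory endpoints, SAP 3.2.3.1 agrees with 4.1 in naming absolute and percent change for the airway-inflammation variables. SAP Section 6 differs: "The three types of change from baseline analyses (absolute, percent, ratio) will be performed for all exploratory endpoints". SAP 4.2.6 gives exploratory variables descriptive statistics and graphs only.

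**The concern.** A fall in cell count cannot go below −100%, but a rise has no ceiling. When the log ratio varies as widely as this plan assumes, a few large rises set the arithmetic mean of percent change. A table could then show a mean near zero, or a mean increase, in an arm whose geometric mean ratio shows a large fall. Neither document says which percent-change statistic to interpret.

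For the primary and secondary variables, the geometric mean ratio appears alongside and corrects the picture. For the exploratory cell counts and biomarkers, a programmer following 4.1 would produce no geometric summary of change, and no model estimate exists to fall back on. A programmer following Section 6 would produce one. The SAP leaves that choice open.

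**Working it through.** **Inputs**

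- Log SDs 1.62 and 1.82 (SAP 1.3): "Given an assumed deviation of the log values in the 2 treatment groups are 1.62 and 1.82". The arms are not assigned and the log base is not stated.
- The SDs describe change in biopsy eosinophils (Protocol 8.2): "The assumptions are based on the change in number of eosinophils per mm"² of subepithelial tissue.
- Effect and power (SAP 1.3): "at least 80% power to detect a 3.5-fold difference versus placebo", two-sided 5%, 31 evaluable per arm.
- Smallest significant difference: 2.4-fold (Protocol 8.2).

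**Reproducing the plan's figures**

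- Pooled SD = √((1.62² + 1.82²)/2) = √((2.6244 + 3.3124)/2) = 1.723.
- Difference on the log scale = ln 3.5 = 1.253.
- Two-sample t-test power (noncentral t) is 79.1% at 30 per arm and 80.4% at 31, which matches the plan's 31.
- Smallest significant fold = exp(t(0.975, 60) × 1.723 × √(2/31)) = exp(2.000 × 0.4376) = 2.40, which matches 2.4.
- By the normal approximation, base-10 logs would need 158 per arm, base-2 logs 15 and natural logs 30. The SDs are therefore natural-log SDs of the change.

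**Expected percent change**

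For a lognormal ratio with log mean μ and log SD s:

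- mean percent change = 100 × (exp(μ + s²/2) − 1)
- median percent change = 100 × (exp(μ) − 1)

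Take the placebo geometric mean ratio as 1. No change then means μ = 0, and the planned effect means μ = −ln 3.5 in the active arm.

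| Case | SD 1.62 | SD 1.82 | Median, either SD |
|---|---|---|---|
| No change | exp(1.3122) − 1 = 3.714 − 1 = **+271%** | exp(1.6562) − 1 = 5.239 − 1 = **+424%** | 0% |
| 3.5-fold reduction | 3.714/3.5 − 1 = **+6%** | 5.239/3.5 − 1 = **+50%** | 1/3.5 − 1 = −71% |

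Under a 3.5-fold fall the expected mean is exactly zero when s = √(2 ln 3.5) = 1.583. Both of the plan's SDs exceed this.

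**Behaviour in a sample of 31 per arm** (100,000 simulated trials)

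| Quantity | Active SD 1.62, placebo 1.82 | Active SD 1.82, placebo 1.62 |
|---|---|---|
| Typical (median) active-arm mean percent change, 3.5-fold effect | −9% | +19% |
| Active-arm mean above zero | 42% of trials | 63% of trials |
| Active-arm median below zero | over 99.8% | over 99.8% |
| Active-arm mean below placebo mean | 98% | 91% |

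With no change, the typical sample mean is about +216% (SD 1.62) or +316% (SD 1.82). This is below the expected value, because the expectation is driven by rare extreme samples.

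**Zero baselines**

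SAP 4.1 replaces a zero baseline by half the smallest non-zero value, m/2, before percent change is formed. Any non-zero later value is at least m, so the percent change is at least 100 × (m − m/2)/(m/2) = 100%. The documents give no data on how often this would occur. The same replacement enters the ratio, where the log dampens it.

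**The case against.** The strongest reply is that nothing inferential is touched, and that is correct. SAP 4.2.4 tests and estimates on the log ratio, and SAP 4.2.5 does the same for the secondary variables. The additional models use absolute change or ranks; none has raw percent change as its response. A reader might infer lost power or a biased primary result, but no test on percent change is planned.

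A reader might also infer that the arithmetic mean is the SAP's only percent-change summary. It is not: the same sentence lists the median, minimum and maximum, and the ratio gets a geometric mean.

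A third inference is that a true reduction would be read as none. The inflation affects both arms, and under these assumptions the tralokinumab mean falls below the placebo mean in 91–98% of simulated trials. The misleading figure is the within-arm mean read alone.

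Three further limits stand. Protocol 8.5 says extreme values might bias an arithmetic mean, but it does not rule the mean out and lists mean and SD among its own summaries. The SDs concern submucosal eosinophils only; no SD is given for blood eosinophils, ECP, IgE, FeNO or the exploratory counts. SAP 4.1 also has a general sentence giving geometric means for continuous variables, which covers values at a visit but does not settle the summary of change for exploratory endpoints.

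What survives is a mean with no guidance on its use, and a direct conflict between 4.1 and Section 6.

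**Conclusion.** The point holds as a descriptive-reporting defect, and correcting it is a free improvement. For submucosal eosinophils, the arithmetic mean percent change has expectation +271% to +424% with no change and +6% to +50% under the planned effect, against medians of 0% and −71%. These figures rest on lognormal ratios, natural-log SDs (confirmed by the sample-size reproduction) and a placebo geometric mean ratio of 1. The plan states only a fold difference versus placebo, so another placebo ratio g would multiply each mean ratio by g.

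The consequence is small for the primary and secondary variables, where the geometric mean ratio is always reported. It is larger for exploratory tissue and sputum cell counts and biomarkers, where descriptive statistics are the main evidence and the SAP disagrees with itself about whether a ratio is summarised. The size of the distortion there cannot be calculated from the documents.

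**What to change.** 1. Amend the allocation sentence in SAP 4.1, and the matching text in 3.2.3.1, so that exploratory cell counts and biomarkers also receive the ratio summary (N, geometric mean, SD of logs) that Section 6 states.
2. For eosinophils and other right-skewed cell or biomarker variables, in 4.1 and 4.2.4, report percent change as 100 × (geometric mean ratio − 1) with its 95% CI, plus median and range.
3. Remove the arithmetic mean and SD of percent change for those variables, or keep them with a footnote that they should not be interpreted.

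The cost is SAP wording and table shells. No new data, assessments or subjects are needed, and the primary and secondary analyses stay as they are.
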